11.1.5 Duration of Response

Duration of overall response: The duration of overall response is measured from the time measurement criteria are met for CR or PR (whichever is first recorded) until the first date that recurrence or PD is objectively documented, taking as reference for PD the smallest measurements recorded since the treatment started.

Duration of overall complete response: The duration of overall CR is measured from the time measurement criteria are first met for CR until the first date that recurrent disease is objectively documented.

Duration of stable disease: Stable disease is measured from the start of the treatment until the criteria for progression are met, taking as reference the smallest measurements recorded since the treatment started.

11.1.6 Response Review

An expert radiologist independent of the study will review all cases to objectively determine response classification.

12. ADVERSE EVENT REPORTING REQUIREMENTS

12.1 Definitions

12.1.1 Adverse Event (AE)

An adverse event (AE) is any undesirable sign, symptom or medical condition or experience that develops or worsens in severity after starting the first dose of study treatment or any procedure specified in the protocol, even if the event is not considered to be related to the study.

Abnormal laboratory values or diagnostic test results constitute adverse events only if they induce clinical signs or symptoms or require treatment or further diagnostic tests.

12.1.2 Serious adverse event (SAE)

A serious adverse event (SAE) is any adverse event, occurring at any dose and regardless of causality that:

• Results in death

• Is life-threatening. Life-threatening means that the person was at immediate risk of death from the reaction as it occurred, i.e., it does not include a reaction which hypothetically might have caused death had it occurred in a more severe form.

• Requires or prolongs inpatient hospitalization (i.e., the event required at least a 24-hour hospitalization or prolonged a hospitalization beyond the expected length of stay). Hospitalization admissions and/or surgical operations scheduled to occur during the study period, but planned prior to study entry are not considered SAEs if the illness or disease existed before the person was enrolled in the trial, provided that it did not deteriorate in an unexpected manner during the trial (e.g., surgery performed earlier than planned).

• Results in persistent or significant disability/incapacity. Disability is defined as a substantial disruption of a person's ability to conduct normal life functions.

• Is a congenital anomaly or birth defect; or

• Is an important medical event when, based upon appropriate medical judgment, it may jeopardize the participant and require medical or surgical intervention to prevent one of the outcomes listed above. Examples of such medical events include allergic bronchospasm requiring intensive treatment in an emergency room or at home; blood dyscrasias or convulsions that do not result in inpatient hospitalization, or the development of drug dependency or drug abuse.

Events **not** considered to be serious adverse events are hospitalizations for:

- routine treatment or monitoring of the studied indication, not associated with any deterioration in condition, or for elective procedures
- elective or pre-planned treatment for a pre-existing condition that did not worsen
- emergency outpatient treatment for an event not fulfilling the serious criteria outlined above and not resulting in inpatient admission
- respite care

12.1.3 Expectedness

Adverse events can be 'Expected' or 'Unexpected.'

12.1.3.1Expected adverse event

Expected adverse events are those that have been previously identified as resulting from administration of the agent. For the purposes of this study, an adverse event is considered expected when it appears in the current adverse event list, the package insert or is included in the informed consent document as a potential risk.

Refer to Section 6.1 for a listing of expected adverse events associated with the study agent(s).

12.1.3.2Unexpected adverse event

For the purposes of this study, an adverse event is considered unexpected when it varies in nature, intensity or frequency from information provided in the current adverse event list, the package insert or when it is not included in the informed consent document as a potential risk.

12.1.4 Attribution

Attribution is the relationship between an adverse event or serious adverse event and the study treatment. Attribution will be assigned as follows:

CONFIDENTIAL

Version date: February 15, 2017

- Definite The AE is clearly related to the study treatment.
- Probable The AE is likely related to the study treatment.
- Possible The AE may be related to the study treatment.
- Unlikely The AE is doubtfully related to the study treatment.
- Unrelated The AE is clearly NOT related to the study treatment.

12.2 Procedures for AE and SAE Recording and Reporting

Participating investigators will assess the occurrence of CTCAE v4.0 grade \geq 3 AEs and SAEs at all participant evaluation time points during the study.

All CTCAE v4.0 grade \geq 3 AEs and SAEs whether reported by the participant, discovered during questioning, directly observed, or detected by physical examination, laboratory test or other means, will be recorded in the participant's medical record and on the appropriate study-specific case report forms.

The descriptions and grading scales found in the revised NCI Common Terminology Criteria for Adverse Events (CTCAE) version 4.0 will be utilized for AE reporting. All appropriate treatment areas should have access to a copy of the CTCAE version 4.0.

A copy of the CTCAE version 4.0 can be downloaded from the CTEP website at:

http://ctep.cancer.gov/protocolDevelopment/electronic_applications/ctc.htm.

12.3 Reporting Requirements

For multi-site trials where a DF/HCC investigator is serving as the principal investigator, each participating investigator is required to abide by the reporting requirements set by the DF/HCC. The study must be conducted in compliance with FDA regulations, local safety reporting requirements, and reporting requirements of the principal investigator.

Each investigative site will be responsible to report SAEs that occur at that institution to their respective IRB. It is the responsibility of each participating investigator to report serious adverse events to the study sponsor and/or others as described below.

12.4 Reporting to the DF/HCC Overall Principal Investigator

12.4.1 Serious Adverse Event Reporting

All serious adverse events that occur after the initial dose of study treatment, during treatment, or within 30 days of the last dose of treatment must be reported to the DF/HCC Overall Principal Investigator on the local institutional SAE form. This includes events meeting the criteria outlined in Section 11.1.2, as well as the following:

- Grade 3 (severe) Events Only events that are unexpected and possibly, probably or definitely related/associated with the intervention.
- All Grade 4 (life-threatening or disabling) Events Unless expected AND specifically listed in the protocol as not requiring reporting.
- All Grade 5 (fatal) Events When the participant is enrolled and actively participating in the trial OR when the event occurs within 30 days of the last study intervention.

CONFIDENTIAL

Note: If the participant is in long term follow up, report the death at the time of continuing review.

Serious adverse events that occur after initial plasma genotyping and before initial dose of study treatment do not need to be reported, unless they are related with the blood draw.

Participating investigators must report each serious adverse event to the DF/HCC Overall Principal Investigator within 24 hours of learning of the occurrence. In the event that the participating investigator does not become aware of the serious adverse event immediately (e.g., participant sought treatment elsewhere), the participating investigator is to report the event within 24 hours after learning of it and document the time of his or her first awareness of the adverse event. Report serious adverse events by telephone, email or facsimile to:

> [name] [contact] Email: [contact] [contact]

Within the following 24-48 hours, the participating investigator must provide follow-up information on the serious adverse event. Follow-up information should describe whether the event has resolved or continues, if and how the event was treated, and whether the participant will continue or discontinue study participation.

12.4.2 Non-Serious Adverse Event Reporting

Non-serious grade 3 or greater adverse events will be reported to the DF/HCC Overall Principal Investigator on the toxicity Case Report Forms. Given that erlotinib is an FDA approved medication for the treatment of advanced NSCLC, adverse events of grade 2 or less should be recorded in the patient's medical record as a part of standard of care but do not need to be reported centrally to the trial.

12.5 Reporting to the Institutional Review Board (IRB)

Investigative sites within DF/HCC will report all serious adverse events directly to the DFCI Office for Human Research Studies (OHRS).

12.6 Reporting to the Food and Drug Administration (FDA)

The DF/HCC Overall Principal Investigator, as holder of the Non-Significant Risk IDE, will be responsible for all communication with the FDA per 21 CFR Part 812.150.

Unexpected fatal or life-threatening experiences associated with the use of the study treatment will be reported to FDA as soon as possible but in no event later than 10 working days after initial receipt of the information.

12.7 Reporting to the NIH Office of Biotechnology Activities (OBA)

N/a

12.8 Reporting to the Institutional Biosafety Committee (IBC)

N/a

CONFIDENTIAL

12.9 Reporting to Hospital Risk Management

Participating investigators will report to their local Risk Management office any subject safety reports or sentinel events that require reporting according to institutional policy.

12.10 Reporting to Astellas

Reportable SAEs include those occurring after the receipt of the first dose of erlotinib until 30 days after receipt of the last dose of erlotinib. These SAEs must be reported to Astellas immediately for a death or life-threatening event, or within 24 hours of notification of PI for other types of SAEs. These time frames also apply to additional information concerning previously submitted reports of an SAE.

Within 24 hours of awareness of a serious adverse event, whether or not related to the study drug, the Investigator will complete and submit a Medwatch 3500A Form to FDA, containing all required information (reference 21 CFR 312.32). The Investigator will submit a copy of this MedWatch 3500A form to Astellas by either e-mail or fax, within the same timeframe. If submission of this SAE to FDA or Astellas or is not possible within 24 hours, the Investigator's local drug safety contact (IRB, etc.) should be informed by phone.

The SAE documentation, including the Medwatch 3500A Form and available source records should be emailed or faxed to:

Astellas Pharma Global Pharmacovigilance – United States Email: [contact] [contact]

The following minimum information is required: -Study number/IIT regulatory identifier -Subject number, sex and age -The date of report -A description of the SAE (event, seriousness of the event) -Causal relationship to the study drug -Follow-up information for the event should be sent promptly (within 7 days) as necessary.

12.11 Monitoring of Adverse Events and Period of Observation

All adverse events, both serious and non-serious, and deaths that are encountered from initiation of study intervention, throughout the study, and within 30 days of the last study intervention should be followed to their resolution, or until the participating investigator assesses them as stable, or the participating investigator determines the event to be irreversible, or the participant is lost to follow-up. The presence and resolution of AEs and SAEs (with dates) should be documented on the appropriate case report form and recorded in the participant's medical record to facilitate source data verification.

For some SAEs, the study sponsor or designee may follow-up by telephone, fax, and/or monitoring visit to obtain additional case details deemed necessary to appropriately evaluate the SAE report (e.g., hospital discharge summary, consultant report, or autopsy report).

Participants should be instructed to report any serious post-study event(s) that might reasonably be related to participation in this study. Participating investigators should notify the DF/HCC Overall Principal

CONFIDENTIAL

Investigator and their respective IRB of any unanticipated death or adverse event occurring after a participant has discontinued or terminated study participation that may reasonably be related to the study.

13. DATA AND SAFETY MONITORING

13.1 Data Reporting

13.1.1 Method

The ODQ will collect, manage, and monitor data for this study.

13.1.2 Data Submission

The schedule for completion and submission of case report forms (paper or electronic) to the ODQ is as follows:

Form	Submission Timeline
Eligibility Checklist	Complete prior to registration with ODQ
On Study Form	Within 14 days of registration
Baseline Assessment Form	Within 14 days of registration
Treatment Form	Within 10 days of the last day of the cycle
Adverse Event Report Form	Within 10 days of the last day of the cycle
Response Assessment Form	Within 10 days of the completion of the cycle required for response evaluation
Off Treatment/Off Study Form	Within 14 days of completing treatment or being taken off study for any reason
Follow up/Survival Form	Within 14 days of the protocol defined follow up visit date or call

13.2 Safety Meetings

The DF/HCC Data and Safety Monitoring Committee (DSMC) will review and monitor toxicity and accrual data from this trial. The committee is composed of clinical specialists with experience in oncology and who have no direct relationship with the study. Information that raises any questions about participant safety will be addressed with the Principal Investigator and study team.

The DSMC will meet quarterly and/or more often if required to review toxicity and accrual data. Information to be provided to the committee may include: up-to-date participant accrual; current dose level information; DLT information; all grade 2 or higher unexpected adverse events that have been reported; summary of all deaths occurring within 30 days for Phase I or II protocols; for gene transfer protocols, summary of all deaths while being treated and during active follow-up; any response information; audit results, and a summary provided by the study team. Other information (e.g. scans, laboratory values) will be provided upon request.

13.3 Monitoring

Involvement in this study as a participating investigator implies acceptance of potential audits or inspections, including source data verification, by representatives designated by the DF/HCC Overall Principal Investigator (or Protocol Chair) or DF/HCC. The purpose of these audits or inspections is to

examine study-related activities and documents to determine whether these activities were conducted and data were recorded, analyzed, and accurately reported in accordance with the protocol, institutional policy, Good Clinical Practice (GCP), and any applicable regulatory requirements.

All data will be monitored for timeliness of submission, completeness, and adherence to protocol requirements. Monitoring will begin at the time of participant registration and will continue during protocol performance and completion.

The sponsor / IND holder will work with the DFCI Clinical Trials Office to secure an appropriate monitoring plan that will include, but not be limited to, the following activities to ensure protocol and regulatory compliance and data integrity. Monitoring will be conducted by independent and qualified monitors. Monitoring activities will include: ongoing reviews of regulatory files, verifying participant eligibility and the consent process on 100% of participants, verifying safety events and study endpoints for all enrolled participants, and an ongoing review of CRF completion and query resolution. During these activities, monitors will assess for trends and perform additional monitoring based on identified areas of need.

14. REGULATORY CONSIDERATIONS

14.1 Protocol Review and Amendments

This protocol, the proposed informed consent and all forms of participant information related to the study (e.g., advertisements used to recruit participants) and any other necessary documents must be submitted, reviewed and approved by a properly constituted IRB governing each study location. Any changes made to the protocol must be submitted as amendments and must be approved by the IRB prior to implementation. Any changes in study conduct must be reported to the IRB. The DF/HCC Overall Principal Investigator (or Protocol Chair) will disseminate protocol amendment information to all participating investigators.

All decisions of the IRB concerning the conduct of the study must be made in writing.

14.2 Informed Consent

All participants must be provided a consent form describing this study and providing sufficient information for participants to make an informed decision about their participation in this study. The formal consent of a participant, using the IRB approved consent form, must be obtained before the participant is involved in any study-related procedure. The consent form must be signed and dated by the participant or the participant's legally authorized representative, and by the person obtaining the consent. The participant must be given a copy of the signed and dated consent document. The original signed copy of the consent document must be retained in the medical record or research file.

14.3 Ethics and Good Clinical Practice (GCP)

This study is to be conducted according to the following considerations, which represent good and sound research practice:

• E6 Good Clinical Practice: Consolidated Guidance www.fda.gov/downloads/RegulatoryInformation/Guidances/UCM129515.pdf

- US Code of Federal Regulations (CFR) governing clinical study conduct and ethical principles that have their origin in the Declaration of Helsinki
 - Title 21 Part 11 Electronic Records; Electronic Signatures www.access.gpo.gov/nara/cfr/waisidx_02/21cfr11_02.html

CONFIDENTIAL

Title 21 Part 50 – Protection of Human Subjects
 www.access.gpo.gov/nara/cfr/waisidx_02/21cfr50_02.html
 Title 21 Part 54 – Financial Disclosure by Clinical Investigators
 www.access.gpo.gov/nara/cfr/waisidx_02/21cfr54_02.html
 Title 21 Part 56 – Institutional Review Boards
 www.access.gpo.gov/nara/cfr/waisidx_02/21cfr56_02.html
 Title 21 Part 312 – Investigational New Drug Application
 www.access.gpo.gov/nara/cfr/waisidx_02/21cfr312_02.html

• State laws

• DF/HCC research policies and procedures http://www.dfhcc.harvard.edu/clinical-research-support/clinical-research-unit-cru/policies-and-procedures/

It is understood that deviations from the protocol should be avoided, except when necessary to eliminate an immediate hazard to a research participant. In such case, the deviation must be reported to the IRB according to the local reporting policy.

14.4 Study Documentation

The investigator must prepare and maintain adequate and accurate case histories designed to record all observations and other data pertinent to the study for each research participant. This information enables the study to be fully documented and the study data to be subsequently verified.

Original source documents supporting entries in the case report forms include but are not limited to hospital records, clinical charts, laboratory and pharmacy records, recorded data from automated instruments, microfiches, photographic negatives, microfilm or magnetic media, and/or x-rays.

14.5 Records Retention

All study-related documents must be retained for the maximum period required by applicable federal regulations and guidelines or institutional policies.

14.6 Multi-center Guidelines

N/A

14.7 Cooperative Research and Development Agreement (CRADA)/Clinical Trials Agreement (CTA)

N/A

15. STATISTICAL CONSIDERATIONS

15.1 Study Design/Endpoints

This single-arm phase II study will treat 30 patients with erlotinib based upon a positive plasma genotyping assay revealing an *EGFR* sensitizing mutation (exon 19 del, L858R). To identify these 30 patients, we will screen 100 patients with newly diagnosed, progressive or recurrent advanced NSCLC that have not yet undergone standard genotyping. This study will examine a novel treatment strategy utilizing rapid plasma genotyping and immediate erlotinib treatment in *EGFR* mutant patients. The study population will be enriched in never/light smokers and patients of Asian race. All patients will undergo

CONFIDENTIAL

rapid plasma genotyping followed by immediate treatment in *EGFR* mutant patients. Standard tissue genotyping will be performed in parallel. Patients will undergo baseline CT imaging which will be repeated every 6 weeks for a total of 24 weeks. Patients positive for an *EGFR* mutation by plasma genotyping but negative by tissue genotyping will undergo an interim CT scan at 4 weeks after initiating erlotinib to confirm response. The primary statistical analysis of response rate will be performed in 30 patients initiating erlotinib therapy based on plasma genotype.

Objective response rate (primary endpoint) among patients with advanced NSCLC harboring an *EGFR* mutation by plasma genotyping and treated with erlotinib, will be evaluated using RECIST 1.1 criteria, and no patients shall be replaced or omitted in the estimation of response rate. Treatment with erlotinib among those who test positive for an *EGFR* mutation via plasma genotyping will be considered worthy of further study if the lower bound of the two-sided 90% exact binomial confidence interval around the objective response rate exceeds 0.40; this is consistent with observing at least 17 responses (CR or PR) among the 30 patients enrolled on the study. If the true but unknown underlying response rate under this treatment paradigm is 0.45, there is a 0.14 chance of calling this study a success; if the response rate is higher (0.65), then the probability of declaring this approach successful is 0.88.

The operating characteristics of this design will be recalibrated if the final number of patients harboring EGFR mutations in plasma is not exactly equal to 30; in this case, a revised decision rule will be fixed such that the lower bound of the two-sided 90% exact binomial confidence interval around the objective response rate will need to exceed 0.40 in order to declare study success.

15.2 Sample Size/Accrual Rate

100 participants recruited over a 2 year period will undergo plasma genotyping for potential treatment with erlotinib on study. It is anticipated that approximately 30 patients will be positive for an EGFR (exon 19 del/L858R) sensitizing mutation by plasma. After recruitment of 50 patients is complete, the accrual rate and number of patients treated with erlotinib will undergo re-assessment for feasibility.

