Following initial validation of this assay in a small group of patients as described above, we retrospectively examined this assay in a larger group of metastatic NSCLC patients with EGFR sensitizing mutations (exon 19 del, L858R) and acquired resistance to EGFR kinase inhibitors. This study compared the test characteristics of our ddPCR-based plasma genotyping assay for the detection of both EGFR sensitizing and the T790M acquired resistance mutation in a cohort of 41 patients with advanced NSCLC who had undergone re-biopsy and standard tissue genotyping for comparison. This revealed 70% assay sensitivity for detection of EGFR T790M and a 93% assay specificity to T790M. In addition, a subset of 15 of these patients underwent serial plasma genotyping after beginning a new line of systemic/targeted therapy. This subset of patients underwent baseline plasma genotyping followed by repeat testing with each treatment cycle. Patients with a partial response to treatment uniformly exhibited decreased levels of *EGFR* cfDNA over time whereas patients without response exhibited stable or increased levels [Figure 2].¹⁴ These data indicate that this assay may also predict treatment outcome as early as 4 weeks after initiating treatment – potentially allowing early treatment modification.

We have subsequently initiated a prospective study of ddPCR-based plasma genotyping in a planned cohort of 340 NSCLC patients in order to assess its ability to accurately detect *EGFR* sensitizing (exon 19 del, L858R), T790M and *KRAS* G12X mutations. These patients include newly diagnosed patients, those with acquired resistance to kinase inhibitors and those undergoing a new line of subsequent treatment. The aims of this study include assessing both test characteristics compared to gold standard tissue genotyping performed on a biopsy specimen as well as correlating change in detectable levels of mutations

during treatment with radiographic response through serial blood testing. This study has accrued 250 patients thus far. Median TAT for plasma ddPCR is 3 days (range 1-5). Specificity of plasma ddPCR is 99% for 19 del/L858R (94/95) and 100% for *KRAS* (82/82), but lower for T790M at resistance (81%, 22/27). Sensitivity

[figure not shown]

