Figure 2: change in *EGFR* mutation copy number in advanced NSCLC patients with (A) and without (B) a partial radiographic response after initiating a new line of therapy (PR – partial response, SD – stable disease, PD – progressive disease per RECIST 1.1).

[figure not shown]

Figure 3: log-fold change in mutation copy number in advanced NSCLC patients correlates with radiographic response in patients treated with both standard chemotherapy and kinase inhibitors (per RECIST 1.1).

of plasma ddPCR is 75% for 19 del/L858R (73/97) and 73% for T790M (30/41) but lower for *KRAS* (62%, 16/26).

Taken together, these previous studies indicate that ddPCR-based plasma genotyping using our validated assay is able to detect *EGFR* sensitizing mutations (exon 19 del, L858R) in metastatic NSCLC with a

high degree of specificity and acceptable sensitivity. A positive result from this assay is thus highly specific for the presence of an *EGFR* mutation and clinically actionable given the very low likelihood of false positive results.

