3.2 Exclusion Criteria

The following attributes will render a participant ineligible for this study:

- 3.2.1 Participants must not have had chemotherapy within the past 10 days.
- 3.2.2 Participants must not have had prior treatment with an EGFR kinase inhibitor, EGFR directed therapy or investigational agent.
- 3.2.3 Participants must not have residual adverse events from previous therapy greater than CTCAE v4.0 grade 2 at the time of registration.
- 3.2.4 Participants must not have symptomatic brain metastases or brain metastases requiring steroids. Asymptomatic brain metastases not requiring steroids are acceptable.
- 3.2.5 Participant must not have a history of allergy to erlotinib.
- 3.2.6 Second primary cancer which is active and requiring treatment.
- 3.2.7 Participants must not be known to be pregnant or breastfeeding.

CONFIDENTIAL

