15.4 Analysis of Secondary Endpoints

From a total of 100 NSCLC patients studied, we estimate that 30 will have an *EGFR* sensitizing mutation (exon 19 del/L858R), respectively, based upon prior prevalence data at our institution. Concordance between tumor and plasma genotyping results will be calculated using a Cohen's kappa. The potential clinical value of the ddPCR genotyping assay will be estimated using:

• Positive predictive value (PPV): To be clinically useful, the PPV must exceed 90% for the plasma assays for *EGFR* and *KRAS* mutations.

• Sensitivity: The sensitivity of each assay must exceed 70% to have clinical value.

• Efficiency: The turnaround time (TAT) between ordering the plasma genotyping and obtaining the result will be compared to the TAT for tumor genotyping. We will compute the turnaround time for each, and compare them using the Wilcoxon-test. To have maximal clinical value, the median TAT for plasma genotyping must be less than 3 days.

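### The plan uses the same 30 of 100 for plasma-positives and for mutation carriers. At its own assay point estimates, 30 carriers give about 23 plasma-positives.

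*Combined protocol and SAP*

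**What the plan says.** Section 15.2 plans to genotype 100 participants and says: "It is anticipated that approximately 30 patients will be positive for an EGFR (exon 19 del/L858R) sensitizing mutation by plasma". The Synopsis, 1.1 and 15.1 build on this by presenting the screening of 100 as the way to find the 30 patients to be treated.

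Section 15.4 uses the same number for something else: "From a total of 100 NSCLC patients studied, we estimate that 30 will have an" EGFR sensitizing mutation, "based upon prior prevalence data at our institution". It does not say whether that prevalence was measured in tissue or plasma, or in an enriched or unselected population.

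Section 2.3 gives the assay's performance against tissue. Sensitivity: "of plasma ddPCR is 75% for 19 del/L858R (73/97"). Specificity: "Specificity of plasma ddPCR is 99% for 19 del/L858R (94/95"). No section applies these figures to the prevalence.

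Section 15.1 declares success if the lower bound of the two-sided 90% exact interval for the response rate exceeds 0.40. At 30 patients it gives this as at least 17 responses, with success probability 0.14 at a true rate of 0.45 and 0.88 at 0.65. If the final number is not 30, the cut-off is reset under the same interval criterion. Section 15.2 adds a feasibility review after 50 patients.

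**The concern.** Having the mutation and testing positive for it in plasma are different events. With few false positives, the two counts agree only if plasma misses almost no carriers. The plan does not expect that: 1.3 makes the false negative rate a secondary objective, and 15.4 asks only that sensitivity exceed 70%.

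What is at stake is the size of the primary analysis set. The stated power of 0.88 belongs to 30 treated patients. If 30 is the number of carriers and screening ends at 100, fewer will be treated and the power is lower. The 50-patient review has no stated expected count to judge against.

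**Working it through.** **Inputs.** Screened 100 (15.2); 30% as prevalence (15.4) or as plasma-positive rate (15.2); sensitivity 73/97 = 0.753 and false-positive rate 1/95 = 0.0105 (2.3); success criterion (15.1). Assumed in the base case: the 2.3 figures carry over, no one enters already known to be plasma-positive, every plasma-positive is treated, and screening stops at 100.

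**1. The plan's own figures at n=30.** The exact lower bound is 0.370 for 16/30 and 0.402 for 17/30, so the cut-off of 17 is right. P(X≥17) is 0.136 at a response rate of 0.45 (stated 0.14) and 0.874 at 0.65 (stated 0.88). Type I error at 0.40 is 0.048.

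**2. Plasma-positives from 30 carriers.** 30 × 73/97 + 70 × 1/95 = 22.6 + 0.7 = 23.3.

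- The exact 95% interval for 73/97 is 0.655 to 0.835, which gives 20.4 to 25.8.
- With the false-positive rate also at its upper exact limit (0.0573): 30 × 0.835 + 70 × 0.0573 = 29.0.
- Sensitivity needed for 30 carriers to give 30 positives: (0.30 − 0.70/95)/0.30 = 0.975.

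**3. Chance of reaching 30.** With a plasma-positive rate of 0.233, P(at least 30 of 100) = 0.07 (5th to 95th percentile of yield 17 to 30). With a rate of 0.30 it is 0.54 (23 to 38).

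**4. Power of the existing rule by number treated.** The cut-off is the smallest count whose exact lower bound exceeds 0.40.

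| n | Cut-off | Power at 0.65 | Power at 0.70 |
|---|---|---|---|
| 20 | 13 | 0.60 | 0.77 |
| 21 | 13 | 0.71 | 0.85 |
| 22 | 14 | 0.65 | 0.81 |
| 23 | 14 | 0.74 | 0.88 |
| 24 | 15 | 0.69 | 0.85 |
| 25 | 15 | 0.77 | 0.90 |
| 26 | 16 | 0.72 | 0.87 |
| 27 | 16 | 0.80 | 0.92 |
| 28 | 16 | 0.86 | 0.95 |
| 29 | 17 | 0.82 | 0.93 |
| 30 | 17 | 0.87 | 0.96 |

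Type I error at 0.40 is at most 0.05 throughout. Power is saw-toothed and n=23 is a local high, so the fairer comparison averages over the random yield:

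| Response rate | 30% is mutation prevalence | 30% is plasma-positive rate |
|---|---|---|
| 0.65 | 0.71 | 0.83 |
| 0.70 | 0.85 | 0.93 |

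Over the interval for sensitivity, the 0.71 ranges from 0.64 to 0.76.

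**5. Known plasma-positives (3.1.2.1).** Suppose 9 enter this way and prevalence is 30% in the other 91. Positives: 9 + 91 × 0.233 = 30.2. At the base-case positive predictive value, 22.6/23.3 = 0.97, carriers are 9 × 0.97 + 91 × 0.30 = 36. The treated number reaches 30, but the carrier figure in 15.4 is then too low. Both 30s hold only near 25 known positives with about 8% prevalence in the other 75: positives 25 + 75 × (0.08 × 0.753 + 0.92 × 0.0105) = 30.2; carriers 25 × 0.97 + 75 × 0.08 = 30.2.

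**6. Other routes to 30.** Prevalence would have to be (0.30 − 1/95)/(73/97 − 1/95) = 0.39, or the number screened 30/0.233 = 129. At an assumed prevalence of 35%, the yield is 27 and P(at least 30) is 0.28.

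**7. The 50-patient review.** 50 × 0.233 = 11.7 expected plasma-positives (5th to 95th percentile 7 to 17), against 15 if 30% is the plasma rate.

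**The case against.** The best defence is that this is loose wording. Section 15.4 names neither assay nor population, and 3.1.4 and 3.3 enrich for carriers. If the 30% is an unenriched rate and enriched prevalence is near 39%, 15.2 is right and only 15.4 needs correcting. A plasma basis is also possible, since a plasma cohort existed: "This study has accrued 250 patients thus far". This stands, and it is why the power loss is conditional. It does not remove the mismatch, because one of the two sections still needs changing.

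A reader might infer that the two figures can never both hold. That goes too far. Both are approximate, and the joint upper limits give 29, though both limits together are unlikely. The sensitivity also comes from a cohort described as follows: "These patients include newly diagnosed patients, those with acquired resistance to kinase inhibitors and those undergoing a new line of subsequent treatment". Section 3.2.2 bars part of that group: "Participants must not have had prior treatment with an EGFR kinase inhibitor, EGFR directed therapy or investigational agent". Applying 73/97 here is therefore an assumption, although it is the only sensitivity for these mutations from that prospective cohort.

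The plan also partly provides for a shortfall. The recalibration in 15.1 controls type I error, and the 50-patient review looks at the number treated. Neither restores power. If screening runs on until 30 are treated, power is unaffected and the 100 becomes the unsupported figure.

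Part of the gap below 0.88 is not due to this mismatch: even a true plasma rate of 30% gives an averaged power of only 0.83.

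**Conclusion.** At the point estimates in 2.3, the figures in 15.2 and 15.4 are not compatible, and known plasma-positives do not reconcile them in any plausible number. The consequence depends on what the 30% means. If it is mutation prevalence in the enrolled population and screening stops at 100, about 23 patients are expected to be treated. Averaged power at a response rate of 0.65 falls by about 12 points (0.83 to 0.71), and at 0.70, the approximate rate cited in 2.4, by about 8 (0.93 to 0.85). Mutation prevalence is the natural reading of 15.4, but the documents do not settle it, so confidence in the power loss is medium.

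A reader might also infer that the 0.88 is miscalculated or that a false claim of success becomes more likely. Neither follows: the figures at n=30 reproduce to within rounding, and type I error stays at or below 0.05 for 20 to 30 patients. This should be fixed, but it does not undermine the decision rule.

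**What to change.** State whether the 30% is a mutation-prevalence or plasma-positive rate in the enriched population, and whether screening stops at 100. Make the Synopsis, 1.1, 15.1, 15.2 and 15.4 agree. Then:

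- **Mutation prevalence, screening stops at 100:** restate the expected treated number as about 23, replace the single 0.88 with the power of the existing rule over about n=20 to 30, and judge the 50-patient review against about 12 plasma-positives.
- **Screening continues until 30 are treated:** keep the power and restate the number screened (about 129 on these assay figures, if 30% is mutation prevalence).
- **Plasma-positive rate:** keep 30 and correct the carrier figure in 15.4 from the sponsor's own data. The 39% above is only what the assay figures imply, not a value to adopt.
- **Known plasma-positives counted on:** state their expected number and correct the carrier figure in 15.4 as well.

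The cost is one or two sentences, consistent numbers and at most a short table. The target of 30 treated patients and the decision rule do not change; only the second option restates the number screened. The downside is that the stated power may become less favourable.
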